Section # and Name	Description of Change	Brief Rationale
1.1 Synopsis	Criteria for cPRA reduction is corrected from “at least 50% increase of likelihood” to “at least 100% increase of likelihood”.	To correct inconsistencies and to align with Section 10.9, Table 13, which defines target cPRA as the reduction of cPRA required to achieve at least 100% increase in the likelihood of a compatible donor (LCD)

1 PROTOCOL SUMMARY

1.1 SYNOPSIS

Protocol title:

A Phase 1b/2 study to evaluate the safety, pharmacokinetics, and preliminary efficacy of isatuximab (SAR650984) in patients awaiting kidney transplantation

Short title:

Safety, pharmacokinetics, and preliminary efficacy of isatuximab in patients awaiting kidney transplantation

Rationale:

About 30% of the kidney transplant waitlist patients are sensitized to human leukocyte antigen (HLA). The HLA sensitized patients are at risk for early graft loss from antibody mediated rejection (AMR) due to the presence of alloantibodies or donor-specific antibodies (DSAs), leading to prolonged wait time because of the lower likelihood of finding a compatible donor compared to those who are not sensitized. Current desensitization therapies (not registered by competent health authorities) aim to overcome the humoral incompatibility by removing or reducing the strength of alloantibodies, but do not target the terminally differentiated antibody-secreting plasma cells which express high level of cluster of differentiation (CD) 38. Isatuximab, an immunoglobulin G1 (IgG1) monoclonal antibody (mAb) directed against CD38, has shown clinical response in relapsed/refractory multiple myeloma patients as a single agent and in combination with immunomodulatory agents, and is being developed in other advanced malignancies. In general, isatuximab is well-tolerated clinically with a manageable safety profile. This study is designed to explore whether isatuximab may have activity in desensitization of patients awaiting kidney transplantation.

Objectives and endpoints

Objectives	Endpoints
Primary	

Phase 1: To characterize the safety and tolerability of isatuximab in kidney transplant candidates.Phase 2: To evaluate the efficacy of isatuximab in desensitization of patients awaiting kidney transplantation.	
Adverse events (AEs)/serious adverse events (SAEs) and laboratory abnormalities.Response rate (RR) defined as the proportion of participants meeting at least one of the predefined desensitization efficacy criteria, from baseline up to 26 weeks after treatment period, measured by single antigen bead (SAB) assay per central laboratory assessment as follows:
Reduction in calculated panel reactive antibodies (cPRA) resulting in at least 100%

Objectives	Endpoints
	
increase of likelihood of finding a compatible donor (for target cPRA, see Section 10.9).
 
- Reduction in antibody titer ($\geq 75\%$ reduction from baseline) to achieve target cPRA (see Section 10.9).- Elimination of ≥ 1 anti-HLA-antibody (ie, mean fluorescence intensity [MFI] reduced to < 2000) as measured by a SAB assay, for antibodies with baseline MFI ≥ 3000.
Secondary	
	
• Phase 2: To characterize the safety profile of isatuximab in kidney transplant candidates.• To characterize the pharmacokinetic (PK) profile of isatuximab in kidney transplant candidates.• To evaluate the immunogenicity of isatuximab.• To assess the overall efficacy of isatuximab in desensitization of patients awaiting kidney transplantation.• AEs/SAEs, and laboratory abnormalities.• PK parameters of isatuximab (see Table 7)• Incidence of anti-drug antibodies (ADA) against isatuximab.• Duration of response (DoR) per central laboratory assessment.• Proportions of participants and duration achieving target cPRA per local laboratory assessment.• Number of anti-HLA-antibody with baseline MFI ≥ 3000 reduced to < 2000 as measured in a SAB assay per central laboratory assessment.• Transplantability including time to first transplant offer, time to transplant, and number of transplant offers, if applicable.• Time to first AMR episode and rate of AMR, if applicable.• Graft survival at 6 months post-transplant, if applicable.

Overall design:

This is a Phase 1b/2 open-label, non-randomized, multi-center study to evaluate the safety, PK, and preliminary efficacy of isatuximab in patients awaiting kidney transplantation. The study will be conducted in 2 phases (see [Figure 1](#) for study design schema):

Phase 1 (safety run-in)

A minimum of 6 safety evaluable participants with cPRA $\geq 80\%$ will be enrolled at the dose level to be tested without interruption in Phase 1. In order to be considered as safety evaluable, participants must have received at least 90% of the planned cumulative doses of the first cycle (unless they discontinue investigational medical product [IMP] due to pre-defined unacceptable toxicity).

Pre-defined unacceptable toxicity is defined as any verified Grade 4 AEs or laboratory abnormalities (except infusion reactions [IR]) occurring during the first cycle of treatment, unless

solely due to the underlying disease or due to a cause obviously unrelated to the IMP, if confirmed by the Sponsor and recruiting Investigators.

The totality of the safety findings, including all AEs occurring during treatment, unless solely due to the underlying disease or due to a cause obviously unrelated to IMP, will be taken into consideration for confirming the Phase 2 dose. Phase 2 of the study will be initiated after 6 safety evaluable participants have completed first cycle observation period where the dose level is determined to be sufficiently well-tolerated.

If the starting dose (SD) is determined not to be sufficiently well-tolerated, 6 additional (minimum) safety evaluable participants will be enrolled at dose level minus 1 (DL-1) (see [Table 1](#) for details on the dose levels and schedule for Phase 1).

Overall safety monitoring will also be performed throughout the conduct of the study.

Upon completion of the first cycle safety observation period for each participant enrolled in Phase 1, participants will continue study procedures until study completion (see “Duration of study period [per participant]” in [Figure 2](#)).

Phase 2

In Phase 2, two cohorts will be included:

Cohort A: Participants with cPRA $\geq 99.90\%$; active candidates on the kidney waitlist. Up to 6 participants with living donor can be enrolled into Cohort A.

Cohort B: Participants with cPRA 80.00% to 99.89%; active candidates on the kidney waitlist with no living donor cleared for donation.

Disclosure Statement: This is a Single Group, Treatment study with 1 arm (2 cohorts) that is not masked. All participants will receive isatuximab monotherapy.

Number of participants:

In Phase 1, approximately 6 to 12 safety evaluable participants are expected to be enrolled (see [Section 9.3](#) for definition of Safety Evaluable Population).

Approximately 24 to 36 participants (Phase 1 and Phase 2) are expected to be enrolled if the SD is retained as the Phase 2 dose or approximately 30 to 42 participants are expected to be enrolled if DL-1 is the Phase 2 dose.

A maximum of 6 replacements per cohort is allowed for participants who:

- enroll in Phase 1 and receive $<90\%$ of the planned cumulative doses within the first cycle (unless they discontinue IMP due to pre-defined unacceptable toxicity), or
- receive $<75\%$ of planned cumulative doses within 3 cycles, or
- have consecutive dose interruption of >28 days, or

- do not complete site visit follow-up period (FUP), after agreement with Medical Monitor.

Intervention groups and duration:

All participants will receive isatuximab monotherapy and the planned treatment duration is 3 cycles (each cycle is 28 days).

Starting dose and de-escalation design:

Starting dose is 10 mg/kg once weekly (QW) for 4 weeks followed by once every 2 weeks (Q2W). If the SD is determined not to be sufficiently well-tolerated, 6 additional (minimum) safety evaluable participants will be enrolled at DL-1. Dose levels and schedule for Phase 1 are detailed in [Table 1](#).

Overall safety monitoring will also be performed throughout the conduct of the study.

Table 1 - Dose level and schedule in Phase 1

Dose Level	Isatuximab
	1 cycle = 4 weeks (28 days)
SD	10 mg/kg QW × 4 for Cycle 1 → Q2W for cycles 2 and 3
DL-1	5 mg/kg QW × 4 for Cycle 1 → Q2W for Cycles 2 and 3

Abbreviations: DL-1 = dose level minus 1, QW = once weekly, Q2W = once every 2 weeks, SD = starting dose

Duration of study period (per participant):

The study will have a screening period of up to 28 days, a treatment period of up to 12 weeks, a site visit FUP of up to 26 weeks, and an extended FUP which include telephone contacts every 90 days and information collection until study cut-off, death, or lost to follow-up. The study cut-off is planned at 26 weeks after the last participant completes the treatment period, or when the last ongoing participant is lost to follow-up, whichever is earlier. The Sponsor may choose to extend the study cut-off date depending on the enrollment rate observed to facilitate adequate follow-up data collection. Participants who wish to proceed to transplantation when a compatible donor becomes available while on study must discontinue IMP immediately, and complete an early discontinuation (E/D) visit prior to transplantation if clinically feasible, and proceed to extended FUP. The study duration that involves site visit per participant (ie, screening, treatment, site visit FUP) will be approximately 42 weeks. The study duration including extended FUP per participant will be approximately 78 weeks (depending when the participant is enrolled).

Treatment period: The cycle duration is 28 days and a complete treatment period is comprised of 3 cycles of IMP treatment. Participants will continue treatment until receiving 3 cycles of IMP, unacceptable AE per Investigator's judgment, or participants' decision to stop the treatment.

Site visit FUP: Participants completing the treatment period and who are able to remain on study will return to the study sites for study procedures.

Extended FUP: The following participants will be followed-up every 90 days by phone calls until study cut-off date, death, or lost to follow-up, whichever comes first:

- Participants who completed or discontinued from site visit FUP
- Participants who proceed to transplantation during treatment period or site visit FUP.

During extended FUP, specified information per protocol will also be collected by the study site (see Schedule of Activities [SoA], [Section 1.3](#)).

Study interventions

Investigational medicinal product

Isatuximab:

- Formulation: Sterile 20 mg/mL concentrate for solution for infusion in single use vials containing 20 mg/mL (500 mg/25 mL) isatuximab in 20 mM histidine, 10% (w/v) sucrose, 0.02% (w/v) polysorbate 80, pH 6.0.
- Route of administration: Intravenous (IV) infusion.
- Dose regimen: Refer to the section above ([Table 1](#)) for Phase 1 dose regimen. Dose for Phase 2 will be determined based on the safety data from Phase 1. The Sponsor may decide to test an isatuximab dose of 20 mg/kg in case of inadequate efficacy and/or PK results.

Noninvestigational medicinal product

Premedication:

All participants will receive the following premedications to prevent or reduce the incidence or severity of IRs, approximately 15 to 30 minutes prior to isatuximab infusion (no longer than 60 minutes). Premedication is mandatory for the first 4 isatuximab infusions (see criteria below for subsequent infusions). The use of ranitidine or equivalent as part of IR premedication is left to the medical judgement of the Investigator. The standard premedication regimen will include:

- Acetaminophen 650 to 1000 mg oral route (PO) (or equivalent)
- Diphenhydramine 25 to 50 mg IV (or equivalent)
- Methylprednisolone 100 mg IV (or equivalent)
- Montelukast 10 mg PO (or equivalent)

Noninvestigational medicinal products (NIMP) will be locally sourced and the formulations may vary.

Premedication for prevention of IR has to be given for the first four isatuximab infusions, and the first infusion using fixed volume infusion following approval of Amended Protocol 01 (applicable for participants enrolled under original Protocol).

For a participant who has no IR upon 4 consecutive infusions, premedication for the subsequent infusions is optional at the Investigator's discretion.

Statistical considerations:

The participants treated at the Phase 2 dose during Phase 1 will be included in the efficacy analysis together with the participants in Phase 2.

- **Sample size calculations**

With a minimum sample size of 12 participants per cohort and 1-sided alpha of 0.025, the analysis will have at least 80% power to demonstrate that the RR is significantly better than █ assuming the true RR is █, based on exact test. A null hypothesis of █ is selected representing placebo control as there is currently no approved or standard therapy for desensitization, and there is no expected decrease in anti-HLA antibody levels or cPRA in patients who do not undergo desensitization therapy.

- **Primary analysis:**

- AEs and laboratory abnormalities in Phase 1 will be listed.
- Response rate by cohort will be summarized using descriptive statistics. A 95% 2-sided confidence interval will be computed using the Clopper-Pearson method.

[figure not shown]
- **Analysis of secondary endpoints:**

- All secondary (if applicable/possible) endpoints will be summarized descriptively and presented by cohort. Categorical variables (eg, rates and proportions) will be tabulated via frequency distributions. Continuous variables (eg, change from baseline) will be summarized by providing the number of observations (n), mean, median, standard deviation, minimum, and maximum. Duration of response (DoR) and other time to event variables will be analyzed using Kaplan-Meier method.
- No hypothesis/significance testing will be performed.

Data Monitoring Committee: No

[figure not shown]
1.2 SCHEMA

Figure 1 - Graphical study design

Abbreviations: cPRA = calculated panel reactive antibodies, DL-1 = dose level minus 1

Figure 2 - Duration of study period (per participant)

1.3 SCHEDULE OF ACTIVITIES (SOA)

Procedure	Screening (up to 28 days before Day 1)	Treatment Period (12 weeks)								Site Visit FUP (26 weeks) ^a	E/D ^b	Extended FUP ^c	Notes All on-treatment procedures should be performed prior to IMP administration unless indicated otherwise				
		Cycle 1 (28 Days)				Cycle 2 (28 days)		Cycle 3 (28 days)									
		D1	D8	D15	D22	D1	D15	D1	D15								
Time Window (days)		±1	±1	±1	±1	±2	±2	±2	±2	±7	±7	±7					
Informed consent	X												Informed consent may be signed prior to D- 28				
Inclusion and exclusion criteria	X																
Demography	X												Date or year of birth (depending on local regulation), sex, ethnicity, and race (if local regulation allows)				
Medical, disease, and surgical history	X												Include start date of dialysis				
Sensitizing events	X	←=====→											Collect dates and types of relevant sensitizing events that can impact cPRA (eg, Blood transfusion)				
HLA tissue typing (collect data on already available results is acceptable)	X												For screening (can be done prior to D-28), enter the most recent results if available				
12-lead ECG	X												See Section 8.2.3				

Procedure	Screening (up to 28 days before Day 1)	Treatment Period (12 weeks)								Site Visit FUP (26 weeks) ^a	E/D ^b	Extended FUP ^c	Notes All on-treatment procedures should be performed prior to IMP administration unless indicated otherwise				
		Cycle 1 (28 Days)				Cycle 2 (28 days)		Cycle 3 (28 days)									
		D1	D8	D15	D22	D1	D15	D1	D15								
Time Window (days)		±1	±1	±1	±1	±2	±2	±2	±2	±7	±7	±7					
Echocardiography	X												Should be performed at dry weight, and/or on a non-dialysis day (see Section 8.2.4)				
Full physical examination including height (screening only) and weight	X (≤7 days prior to first IMP)	X		X		X		X		X (Weeks 1 and 9 only)	X		See Section 8.2.1				
Vital signs ^d	X	X	X	X	X	X	X	X	X	X (Weeks 1 and 9 only)	X		See Section 8.2.2)				
Pregnancy test (WOCBP)	X (≤7 days prior to first IMP)					X		X		X ^e (Week 1, and 5 months after last dose)	X ^e		Serum pregnancy test at screening; serum or urine hCG pregnancy test at other time points See Section 10.2				
HBV, HCV, HIV, CMV, EBV	X	As clinically indicated								X ^f	X ^g		See Section 10.2				
Laboratory assessments (blood chemistry, hematology)	X (≤14 days prior to first IMP)	X ^h		X		X		X		X (Weeks 1 and 9 only)	X		See Section 10.2				
Coagulation	X (≤14 days prior to first IMP)	As clinically indicated											See Section 10.2				
Blood typing interference test ⁱ	X (≤14 days prior to first IMP)					X ^j (IAT)				X ⁱ (IAT)			See Section 10.10				

Procedure	Screening (up to 28 days before Day 1)	Treatment Period (12 weeks)								Site Visit FUP (26 weeks) ^a	E/D ^b	Extended FUP ^c	Notes All on-treatment procedures should be performed prior to IMP administration unless indicated otherwise				
		Cycle 1 (28 Days)				Cycle 2 (28 days)		Cycle 3 (28 days)									
		D1	D8	D15	D22	D1	D15	D1	D15								
Time Window (days)		±1	±1	±1	±1	±2	±2	±2	±2	±7	±7	±7					
cPRA and SAB assay (local laboratory assessment)	X	Perform as per local standard of practice												For unacceptable antigens, use MFI ≥2000 as positivity cut-off, and report cPRA to 2 decimal point (eg, 99.90%) See Section 8.1.2			
Blood draw for cPRA and SAB assay (central laboratory assessment)		X ^j				X		X		X (every 4 weeks) ^k	X			Refer to laboratory manual for details			
Blood draw for serum immunoglobulin levels (central laboratory assessment)		X ^j						X		X (Week 17 only) ^k	X ^l			Refer to laboratory manual for details			
Blood draw for immune cell profiling (central laboratory assessment)		X ^j						X		X (Week 17 only) ^k	X ^l			Refer to laboratory manual for details			
Blood draw for functional immune cell assay (central laboratory assessment)		X ^j						X		X (to be collected on Site Visit FUP Week 1 or E/D, if C3D1 sample not collected)				Refer to laboratory manual for details			
Isatuximab		X	X	X	X	X	X	X	X								
PK/ADA		See Pharmacokinetic/ADA Flowchart												See Section 1.3.1			

Procedure	Screening (up to 28 days before Day 1)	Treatment Period (12 weeks)								Site Visit FUP (26 weeks) ^a	E/D ^b	Extended FUP ^c	Notes All on-treatment procedures should be performed prior to IMP administration unless indicated otherwise				
		Cycle 1 (28 Days)				Cycle 2 (28 days)		Cycle 3 (28 days)									
		D1	D8	D15	D22	D1	D15	D1	D15								
Time Window (days)		±1	±1	±1	±1	±2	±2	±2	±2	±7	±7	±7					
AE review	X	←=====→								X (beyond 30 days after last dose of IMP: only ongoing related AEs, new related AEs until resolution/ stabilization)	Stabilization is defined as an AE ongoing without any change for at least 3 months						
SAE review	X	←=====→								X (beyond 30 days after last dose of IMP: only ongoing SAEs, new related SAEs until resolution/ stabilization)							
Prior/concomitant/post medication ^m	X	←=====→								X	X	X	See Section 6.5				
Participant/Transplant (if applicable) Status	X ⁿ	X ⁿ								X ^o	X ^o						

Abbreviations: ADA = anti-drug antibody, AE = adverse event, CMV = cytomegalovirus, cPRA = calculated panel reactive antibodies, D = Day, EBV = Epstein-Barr virus, ECG = electrocardiogram, E/D = early discontinuation, FUP = follow-up period, HBV = hepatitis B virus, hCG = human chorionic gonadotropin, HCV = hepatitis C virus, HIV = human immunodeficiency virus, HLA = human leukocyte antigen, ID = identification number, IMP = investigational medicinal product, MFI = mean fluorescence intensity, PK = pharmacokinetics, SAB = single antigen bead, SoA = Schedule of Activities, SAE = serious adverse event, WOCBP = women of childbearing potential.

- a Week 1 visit for site visit FUP will occur 15 days after Cycle 3 Day 15 (± 7 days), or 15 (± 7 days) after the last dose of IMP if participant discontinued IMP. Depending on local arrangements and preference of the Investigator, site visit FUP procedures may be performed at the study site or at the participant's home by a health care professional. Study procedures not performed at the study site must also be documented in the source documents and recorded in the appropriate pages of the eCRF by the study site.
- b For E/D, study procedures will be performed 30±7 days after last IMP administration if discontinued study during treatment period, or within 30 days if discontinued during site visit FUP. Participants who discontinued IMP but remain on the study and proceed to complete site visit FUP do not need to complete E/D. Participants who wish to proceed to transplantation when a compatible donor becomes available while on study must discontinue IMP immediately, and complete an E/D visit prior to transplantation if clinically feasible, and proceed to extended FUP.
- c In addition to the phone calls every 90 days, study site will collect information per the SoA throughout the extended FUP.
- d Vital sign assessment includes blood pressure, pulse rate, temperature, and respiratory rate. During the treatment period, vital signs should be obtained prior to start of each IMP infusion, 1 hour after start of infusion, at the end of infusion, and during the infusion if clinically indicated.
- e Pregnancy test can be performed at home for participants during the FUP or if date of test does not match with FUP visit and the site must record this in the source document. Test should be performed at the end of isatuximab treatment (ie, Week 1 of site visit FUP or E/D visit [± 7 days]), and 5 months (± 7 days) after the last dose of IMP.
- f Post-treatment tests are only applicable for HBV, CMV, and EBV, and only has to be performed at Site Visit FUP Week 9 if baseline result is positive or as clinically indicated. In case HBV vaccination will be started before first study treatment administration, anti-HBs should be monitored at approximately 1, 2, and 3 months after end of vaccination (± 7 days, or at the next blood sampling). For participants with positive anti-HBc and negative HBsAg and undetectable HBV deoxyribonucleic acid (DNA) at study entry (past resolved infection, resolving acute infection, or receiving antiviral treatment with controlled infection), close monitoring of viral reactivation (greater than 1log10 IU/mL increase in HBV DNA or reappearance of HBsAg or detection of HBV DNA in patients with resolved infection) throughout and following the end of study

treatment should be proposed (alanine aminotransferase [ALT], aspartate aminotransferase [AST], and HBV DNA at Site Visit FUP Week 9 and Week 25, or until initiation of further desensitization therapy/transplant surgery). In case of viral reactivation during study treatment (greater than 1log10 IU/mL increase in HBV DNA or reappearance of HBsAg or detection of HBV DNA in participants with resolved infection), close monitoring of ALT and AST approximately every month (may coincide with the next scheduled blood sampling \pm 7 days), up to study treatment discontinuation. HBV DNA to be done as per Investigator's and/or specialist advice.

- g Only if screening result is positive and not tested during site visit FUP.
- h Assessment not required to be repeated prior to Cycle 1 Day 1, if screening assessments were performed within 7 days prior to the first IMP infusion and met the entry criteria. Window for assessment is within 1 working day prior to IMP infusion.
- i Blood type (if not already done) and phenotype (according to the site protocol). Recommended phenotype includes Rh system (C/c and E/e), Kell system (K/k); Duffyn system (Fya/Fyb); Kidd system (Jka/Jkb); MNS system (M/N, S/s), and indirect antiglobulin test (IAT; indirect Coombs test). Blood type card will be kept by the participant with the study card. Blood type and blood product transfusions are to be recorded in the electronic case report form. The blood bank needs to be informed that the participant is receiving a treatment with an anti-CD38 and a potential interference with the Coombs test is possible (see [Section 10.10](#)). IAT (indirect Coombs test) to be repeated at C2D1 (if not performed at this visit, it can be done at the next blood sampling); if post-treatment (ie, C2D1) IAT (indirect Coombs test) is positive, subsequent tests to be performed at site Visit FUP Weeks 1, 13, and 25, and E/D if discontinued during Site Visit FUP.
- j Blood sample must be collected prior to IMP administration. Window for assessment is within 1 working day prior to IMP infusion.
- k Blood draw time points that do not coincide with site visits may be collected at the local facility or at the participant's home by a health care professional (depending upon local arrangements and preference of the Investigator), provided that samples are collected with designated tubes and per laboratory manual. Blood drawn should be performed prior to dialysis (if dialysis is performed on the same day).
- l Only if site visit FUP sample (ie, Week 17) not collected.
- m Include any desensitization therapy. For participants who proceed to transplantation after E/D, or completion of treatment and/or site visit FUP, also collect immunosuppression regimen.
- n Collect the following information: Start and end date(s) when listed as active candidate on the waitlist for kidney transplant, waitlist ID and transplant center code (if applicable, and if local regulation allows and in line with the most recent participant signed informed consent form), virtual or donor-specific cross matching results, and dates of all transplant offers (if any, indicate whether offers were accepted and reasons of rejecting offers).
- o Collect the following information: Start and end date(s) when listed as active candidate on the waitlist for kidney transplant (if status has changed), virtual or donor-specific cross matching results, dates of all transplant offers (if any, indicate whether offers were accepted and reasons of rejecting offers), solid organ transplant surgery, participant survival status, graft survival status, dates of biopsy proven acute rejection episodes (antibody mediated and/or T-cell mediated), and estimated glomerular filtration rate (eGFR) using the Modification of Diet in Renal Disease (MDRD) equation.

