HBV vaccination could be considered, following investigator's discretion, for patients with negative HBsAg, total anti-HBc, anti-HBs and HBV-DNA. At least 3 doses of vaccine will be administered at monthly intervals, the first one 1-2 weeks before start of study treatment. Anti-HBs should be monitored at approximately 1, 2 and 3 months after end of vaccination (± 7 days, or at the next blood sampling). Anti-HBs above 100 mU/mL will indicate a good seroconversion, between 10 and 100 mU/mL moderate seroconversion that can be limited in time, less than 10 mU/mL will indicate no response to vaccination.

If antiviral therapy for HBV or HCV was started before initiation of IMP and patient was eligible for the trial, the antiviral therapy for HBV or HCV should continue throughout the treatment period as recommended by specialist or Investigator.

See [Section 6.6.3](#) in case of hepatitis B viral reactivation (sub section "Guidance in case of hepatitis B reactivation occurring under study treatment").

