In case of viral reactivation during study treatment (greater than $1\log_{10}$ IU/mL increase in HBV DNA or reappearance of HBsAg or detection of HBV DNA in patients with resolved infection*), study treatment will be held and specialist should be consulted for initiation of anti-viral treatment and monitoring of the patient. Re-start of study treatment should be agreed between sponsor, investigator and specialist (hepatologist) if controlled infection. Close monitoring of ALT and AST approximately every month (may coincide with the next scheduled blood sampling ± 7 days) up to study treatment discontinuation. HBV DNA to be done as per Investigator's or specialist advice.

** Previous known history of acute or chronic hepatitis B or the presence of total anti-HBc with/without anti-HBs; HBsAg negative; undetectable serum HBV DNA; normal ALT levels.*

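### The hepatitis B hold rule depends on HBV DNA and HBsAg, but neither has a dated test in the treatment period for the at-risk subgroup

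*Protocol*

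**What the plan says.** In the Schedule of Activities (Protocol Section 1.3), the row for HBV, HCV, HIV, CMV and EBV has a screening test. For the whole treatment period the entry is "As clinically indicated". Follow-up testing is governed by footnote f and early discontinuation by footnote g.

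For participants who are anti-HBc-positive, HBsAg-negative and HBV-DNA-undetectable at entry, footnote f asks for close monitoring of viral reactivation "throughout and following the end of study" treatment. The text continues "treatment should be proposed (alanine aminotransferase [ALT], aspartate aminotransferase [AST], and HBV DNA at Site Visit FUP Week 9 and Week 25". No other date is given, and HBsAg has none. Footnote g limits the test at the early discontinuation visit: "Only if screening result is positive and not tested during site visit FUP".

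Section 6.6.3 defines reactivation on treatment by three findings: a rise in HBV DNA of more than 1 log10 IU/mL, HBsAg returning, or HBV DNA becoming detectable in resolved infection. It then says "study treatment will be held and specialist should be consulted for initiation of anti-viral treatment and monitoring of the patient".

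Two further places bear on timing. Section 2.3.3 describes viral monitoring before and after treatment and does not mention the period in between. Table 11 footnote a (Section 10.2) lets sites decide which serology and viral load tests are needed.

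**The concern.** The protocol states an aim (watch for reactivation throughout treatment) and an action (hold isatuximab), but schedules no test that links the two while infusions are being given. Monthly ALT/AST checks are prescribed only once a reactivation has been found. ALT and AST are not among the findings that trigger the hepatitis B hold.

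If a reactivation produces neither a transaminase rise nor signs, and the site has no reason of its own to test, nothing scheduled would reveal it before the last infusion. The participant would go on receiving a plasma-cell-depleting antibody when the protocol's own rule says to stop and call a specialist.

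**Working it through.** **Inputs.** Dosing is weekly × 4 in Cycle 1, then every 2 weeks in Cycles 2 and 3, with 28-day cycles (Table 1). This gives 4 + 2 + 2 = 8 infusions. FUP Week 1 is 15 ± 7 days after C3D15 (Section 1.3, footnote a). The PK/ADA flowchart (Section 1.3.1.2) labels FUP Week 9 as D60, and its footnote b sets the matching ADA sample for early leavers at 60 days after the last dose. The early discontinuation visit is 30 ± 7 days after the last dose for those leaving during treatment (footnote b of Section 1.3). On-schedule dosing is assumed, with C1D1 = day 1.

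| Visit | Study day | Infusion | ALT/AST dated | HBV DNA or HBsAg dated |
|---|---|---|---|---|
| C1D1 | 1 | 1 | yes (a recent screening panel may serve) | no |
| C1D8 | 8 | 2 | no | no |
| C1D15 | 15 | 3 | yes | no |
| C1D22 | 22 | 4 | no | no |
| C2D1 | 29 | 5 | yes | no |
| C2D15 | 43 | 6 | no | no |
| C3D1 | 57 | 7 | yes | no |
| C3D15 | 71 | 8 | no | no |
| FUP Week 1 | 71 + 15 = 86 (79–93) | – | yes | no |
| FUP Week 9 | 131 or 142 (124–149) | – | yes | yes |

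**The plan's own date for FUP Week 9.** Counted from infusion 8, the flowchart gives 60 days, so day 71 + 60 = 131. Footnote a gives 15 + 8 × 7 = 71 days, so day 71 + 71 = 142. The two differ by 11 days, so a range is used. With ±7 days it runs from 60 − 7 = 53 to 71 + 7 = 78 days after infusion 8.

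**Length of the gap.** FUP Week 9 is 131 − 1 = 130 to 142 − 1 = 141 days after the first infusion. If the screening sample was taken 28 days before the first infusion, the interval between dated HBV tests is 158 to 169 days. For someone who leaves the study during treatment, the first dated test is 23 to 37 days after the last dose, when dosing has already stopped.

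**Counts.** Dated HBV DNA or HBsAg tests from first to last infusion: 0. Dated ALT/AST after day 1 and before the last infusion: 3 (days 15, 29, 57).

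Two readings of footnote f are possible. The Week 9 and Week 25 dates may be meant to cover both the on-treatment and post-treatment parts, or only the post-treatment part. Either way the on-treatment count is 0.

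**What a dated test could change.** A result available before infusion 5 (C2D1) leaves infusions 5 to 8, so up to 4 of 8 could be held. Before infusion 7 (C3D1) it leaves 7 and 8, so up to 2 of 8. If the result comes back only after that day's infusion, these become 3 and 1.

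**The case against.** The case against change is that this subgroup is already protected in several ways.

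- **Prophylaxis.** Antiviral prophylaxis before the first dose is required (Section 2.3.3, E 09). Both places carry it at least through treatment, and Section 6.5 adds that "the antiviral therapy for HBV or HCV should continue throughout the treatment period as recommended by specialist or Investigator".
- **Transaminases.** ALT/AST are dated through treatment and must be reviewed by the Investigator. Under Table 5, an ALT/AST rise recorded as a Grade 2 or 3 non-hematological adverse event delays dosing on its own, without any HBV result.
- **Site duty.** Table 11 footnote a gives discretion for the purpose of adequate reactivation monitoring. A site doing no on-treatment virology here would sit badly with footnote f.
- **Frequency.** Nothing in the documents supports a monthly virology schedule before a reactivation. The monthly interval in Section 6.6.3 is for ALT/AST afterwards, and HBV DNA is discretionary even then.

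Much of this stands. It makes an undetected case unlikely, and the choice of test frequency is a judgement. It does not close the gap. Prophylaxis lowers the risk but does not show whether virus has returned, and the sponsor itself dated HBV DNA at Weeks 9 and 25. E 09 also admits HBsAg-negative participants whose HBV DNA was positive during screening and then became negative; those who are anti-HBc-positive can fall under footnote f. The ALT/AST and Table 5 routes need a transaminase rise. Site discretion sets an aim but no dates, so practice can differ between sites. The anti-HBs checks at 1, 2 and 3 months follow vaccination, which Section 6.5 offers only to anti-HBc-negative patients.

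**Conclusion.** The concern holds. The missing on-treatment dates are a matter of reading the schedule and are not in doubt. The exposed case is narrow: a reactivation despite prophylaxis, with no transaminase rise and no signs, at a site that does not test unprompted.

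Its frequency cannot be sized. The documents give neither the share of anti-HBc-positive participants nor a reactivation rate under prophylaxis, and among the 24 to 42 planned participants the number may be zero. The hold rule itself is sound; it lacks a scheduled test to trigger it in that one situation. The change is worth making as an inexpensive safety improvement.

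**What to change.** In the Schedule of Activities virology row and footnote f, add HBV DNA and HBsAg at C2D1 and C3D1, before infusions 5 and 7, for participants who enter anti-HBc-positive, HBsAg-negative and HBV-DNA-undetectable. Both markers are proposed because the hold rule names both. Keep testing on clinical indication for additional samples and for everyone else.

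The two visits are 57 − 29 = 28 days apart, similar to the interval Section 6.6.3 uses after a reactivation ("Close monitoring of ALT and AST approximately every month"). The sponsor may prefer another frequency.

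The change can go into the next protocol amendment. It needs 2 + 2 = 4 assays per affected participant, possibly an extra tube, and no extra visit, since chemistry is already drawn on both days. If 0 to 10% of 24 to 42 participants are affected (an assumption, not a figure in the documents), the total is between 0 and 42 × 0.10 × 4 = 16.8, or about 17 assays.
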